#### Sample Size

We will enroll a sample size of at least 2500 participants. This sample size will provide adequate statistical power to achieve our aims. We anticipate an annual event rate of 2.5% based on previous reported results [Lucas 2007; Lucas 2008]. Therefore, over 4 years, we anticipate 10% of participants will meet our primary outcome of eGFR decline. As we do not know the exact incidence of eGFR decline, we provide the minimal detectable difference based on this event rate and also for 8% and 15% incidence of eGFR decline (ie, annual event rates of 2% and 3.75%, respectively). Based on sample size of 2500 participants (50% randomized to pitavastatin and 50% placebo), a two-tailed alpha error of 5% and assuming 5% of participants will be lost during follow-up, we will have 90% statistical power to detect clinically relevant differences in the cumulative incidence of eGFR decline across randomization arms. For example, if 10% of participants randomized to placebo develop our primary endpoint over the 4-

year follow-up period, we will have 90% power to detect an absolute reduction in incidence of 3.6% associated with pitavastatin (10% in placebo vs. 6.4% in pitavastatin arm; **Table 1**). Given that albuminuria is anticipated to be a more frequent endpoint than  $\geq 30\%$  eGFR decline, we will have 90% power to detect clinically relevant differences in the percentage of participants developing this outcome measure. Previous RCTs of pitavastatin in individuals with diabetes and persons with hyperlipidemia demonstrated a 52% and 67% reduction in measures of albuminuria, respectively [Nakamura 2005; Yagi 2011]. Although we expect to see at least a 50% reduction in albuminuria in the pitavastatin group (from 15% to 7.5%) and a modest increase in prevalence of albuminuria in the placebo group [Szczech 2010], we will be powered to detect smaller differences.

Table 1. Minimal detectable difference in incidence of CKD endpoint in REPRIEVE participants randomized to pitavastatin vs placebo.

	Proportion of control population developing CKD		
Aim 1A eGFR decline	8%	10%	15%
90% statistical power	3.2%	3.6%	4.3%
80% statistical power	2.6%	3.2%	3.5%
	Proportion of control population with albuminuria		
Aim 1B % with albuminuria	15%	20%	25%
90% statistical power	4.3%	4.9%	5.4%
80% statistical power	3.8%	4.3%	4.7%

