**OBJECTIVE 2: Assess whether the effect of pitavastatin on CKD is stronger in high-risk groups defined by older age, black race, hypertension, lower CD4 cell counts, or the use of TDF-containing regimens.** We will divide the cohort based on the median age to evaluate differences between the groups above and below the median age. Similar dichotomous approaches will be taken for black race, hypertension (systolic blood pressure  $\geq 140$  mmHg, diastolic blood pressure  $\geq 90$  mmHg or antihypertensive medication use), and TDF-containing regimens. Within each sub-group studied, participant characteristics will be calculated by randomization assignment (pitavastatin or placebo). The percentage of participants developing  $\geq 30\%$  eGFR decline and separately, with ACR  $> 30$  mg/g during follow-up will be calculated for participants randomized to pitavastatin and, separately, their counterparts randomized to placebo. The statistical significance of differences within sub-groups will be calculated using interval censored regression models and chi-square tests as described in Aim 1 above. We will use multiplicative interaction terms (eg, black race \* pitavastatin) to assess differences in the effect of pitavastatin on CKD across sub-groups. We will evaluate CD4 count as a continuous variable to determine if there is a threshold below which statin therapy has greater benefit for kidney function. We will model the interaction between pitavastatin versus placebo and CD4 count as a continuous variable with interval censored regression models and logistic regression for the cumulative incidence [Howard 2011].

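### Appendix V, Objective 2 cuts age at the cohort median to test effect modification, though it models CD4 continuously; if the effect is graded with age, the cut discards roughly 25% to 45% of the information

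*Protocol*

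**What the plan says.** Appendix V, Objective 2 is introduced as follows: "Assess whether the effect of pitavastatin on CKD is stronger in high-risk groups defined by older age". Black race, hypertension, lower CD4 counts and TDF-containing regimens follow in the same list.

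- **Age:** "We will divide the cohort based on the median age to evaluate differences between the groups above and below the median age". Race, hypertension and TDF use are also handled as two-level factors.
- **Test of modification:** multiplicative interaction terms are used "to assess differences in the effect of pitavastatin on CKD across sub-groups".
- **CD4:** "We will evaluate CD4 count as a continuous variable to determine if there is a threshold below which statin therapy has greater benefit". The interaction is then modelled with "CD4 count as a continuous variable with interval censored regression models and logistic regression for the cumulative incidence".

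Race and TDF use are naturally two-level, and hypertension is defined by fixed pressure limits or medication. Age is the only modifier whose cut point depends on who enrolled. Objective 2 names no continuous-age analysis. The SAP supplied covers the CCTA substudy (A5333s) only and does not address the kidney study.

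**The concern.** Age is recorded for every participant, across an eligible range of 40 to 75 years. A median split treats a 40-year-old and someone just under the median as alike, and does the same for someone just over the median and a 75-year-old. If the treatment effect changes gradually with age, the comparison of two halves uses only part of the evidence on that change.

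Interaction tests are already the least informative part of such a study. At the planned rates the whole study expects about 1187.5 × (0.10 + 0.064) ≈ 195 eGFR-decline events. The appendix's power table covers only the overall arm comparison, and no power is stated for any interaction. At stake is how a null age result is read: it could be taken as evidence against a stronger effect in older participants when the test had less power than the data allowed.

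**Working it through.** **1. Inputs from the documents (Appendix V, Sample Size).** N = 2500 randomised 1:1; "a two-tailed alpha error of 5% and assuming 5% of participants will be lost during follow-up". Evaluable: 2500 × 0.95 = 2375, or 1187.5 per arm. Rates for the eGFR endpoint: "10% in placebo vs. 6.4% in pitavastatin arm". Odds ratio = (0.064/0.936)/(0.10/0.90) = 0.615.

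**2. The plan's own figure.** Two-proportion test, two-sided 5%, 1187.5 per arm, mean rate 0.082:
- null SE = √(2 × 0.082 × 0.918 / 1187.5) = 0.01126
- alternative SE = √((0.10 × 0.90 + 0.064 × 0.936) / 1187.5) = 0.01124
- power = Φ[(0.036 − 1.96 × 0.01126) / 0.01124] = Φ(1.24) = 89.3%

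The stated 90% for the main effect is reproduced. It says nothing about interactions.

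**3. Information kept by a median split.** Suppose the log odds ratio for treatment is linear in age. The split test's noncentrality is then approximately the continuous test's times √E, where E = corr(age, age > median)² = Δ²/(4σ²). Here Δ is the difference in mean age between the two halves and σ is the SD of age.
- Uniform on 40–75: Δ = 17.5, σ² = 35²/12 = 102.1, so E = 306.25/408.3 = 0.75.
- Normal: Δ = 2σ√(2/π), so E = 2/π = 0.64. Truncated to 40–75 (for example mean 50, SD 6 before truncation), E ≈ 0.66.
- Right-skewed (exponential truncated to 40–75): E = 0.585 with mean 48.9; E = 0.55 with mean 47.6.

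The loss of information is therefore about 25%, 35% and up to 45%. The age shapes are assumptions, because the documents give only the 40–75 range.

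**4. What this means in power points.** If the continuous test had 80% power, its noncentrality is 1.96 + 0.84 = 2.80. The split then has:
- E = 0.75: Φ(2.80 × 0.866 − 1.96) = 68%, a loss of 12 points
- E = 0.64: Φ(2.80 × 0.798 − 1.96) = 61%, a loss of 19 points
- E = 0.55: Φ(2.80 × 0.740 − 1.96) = 54.5%, a loss of 25.5 points

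**5. Check at this study's size.** Large-sample Wald power for the logistic interaction with n = 2375, placebo risk 10%, odds ratio 0.615 at mean age, and an assumed age main effect of 0.4 log odds per SD. Entries are continuous → split power in %, with points lost in brackets.

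| Assumed interaction (log odds per SD of age) | Uniform | Truncated normal (50, 6) | Skewed, mean 48.9 | Skewed, mean 47.6 |
|---|---|---|---|---|
| 0.15 | 16→13 (3) | 17→12 (5) | 19→13 (7) | 20→12 (8) |
| 0.20 | 24→19 (5) | 26→18 (8) | 30→19 (11) | 31→18 (13) |
| 0.35 | 60→48 (12) | 62→45 (18) | 67→45 (22) | 68→43 (25) |
| 0.45 | 81→69 (12) | 83→65 (18) | 84→64 (21) | 85→62 (23) |

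Simulation of the 0.35 and 0.45 settings (2000 runs each) gave losses of 12, 17 to 18, and 25 to 26 points for uniform, normal and right-skewed age.

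**6. How large those slopes are.** At 0.35 per SD the odds ratio runs from 0.615 × e^0.35 = 0.87 at one SD below mean age to 0.615 × e^−0.35 = 0.43 at one SD above. At 0.45 it runs from 0.96 to 0.39. At 0.20 it runs from 0.75 to 0.50.

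**7. The reverse case.** If the true effect stepped exactly at the median, the roles swap. When the split has 80% power, the linear-age test has 61% (E = 0.64) to 68% (E = 0.75).

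**The case against.** The strongest defence has four parts.

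*The objective is about groups, and CD4 has its own purpose.* Objective 2 speaks of high-risk groups, and CD4 is kept continuous to look for a threshold. The general analysis paragraph of Appendix V also names hypertension, age, race and tenofovir as the subgroups, without CD4. This explains the layout and means the plan does not contradict itself. It does not justify the age cut, since lower CD4 stands in the same list of high-risk groups and is still modelled continuously.

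*The split is a valid prespecified choice.* The rule is fixed before outcomes are seen, balances group sizes, keeps the type I error and assumes no functional form. All of that stands. A reader might infer that the age test is biased or invalid; it is neither. The issue is efficiency under a graded effect, and a step at the median would favour the split. Nothing in the documents suggests such a step.

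*The size depends on assumptions.* This stands in full. A reader might infer a fixed cost of 11 to 25 points. The documents do not support that: they give no interaction size, interaction power or age distribution. Losses that large need steep slopes, and the upper end also needs strongly right-skewed age.

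*The stakes are low and other material is unseen.* Age is one of five modifiers in an ancillary objective, and Protocol 9.6.1 promises cautious reading of supporting analyses. A separate kidney analysis plan might add continuous age, which cannot be excluded. These points limit the weight of the concern but do not remove the loss.

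**Conclusion.** The concern holds as a conditional efficiency point. Appendix V cuts age at a sample-dependent value for its effect-modification test, gives no reason, and already has a continuous-interaction model in the same paragraph.

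- **Information lost under a steady age effect:** about 25% (uniform age), 35% (roughly normal) and up to 45% (strongly right-skewed).
- **Power lost:** about 12 to 18 points for uniform-to-normal age, and up to about 25 if right-skewed, when the continuous test has about 60% to 85% power. For interactions of 0.15 to 0.20 log odds per SD it is roughly 3 to 12 points (13 at the most skewed shape tried), with continuous power of only about 16% to 31%, so both tests are underpowered.

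These figures rest on an effect linear in age on the log-odds scale, assumed age shapes and assumed slopes. The main kidney comparison and the trial's primary endpoint are not affected. Severity is minor to moderate.

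**What to change.** In Appendix V, Objective 2, or in the kidney study's own analysis plan, make the treatment-by-age interaction with age continuous the test of modification. Use the interval-censored and logistic models already specified for CD4, with age linear and a simple spline as a check on shape. Report the estimated pitavastatin effect with a confidence interval at a few prespecified ages, for example 45, 55 and 65. Keep the percentages above and below the median as a descriptive table.

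The change is about one sentence and needs no new data, visits or methods. Its price is the assumption that the effect changes smoothly with age, which costs power if the truth is an abrupt step near the median; the spline and the descriptive table would help to show that.

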**OBJECTIVE 3: To determine whether the effect of pitavastatin on kidney function is mediated through anti-inflammatory effects.** This analysis will follow the traditional case-cohort design. The case-cohort design combines the advantages of cohort studies and case-control analyses. In a case-cohort design, the comparison group is not defined on the basis of the "absence" of the outcome ( $\geq 30\%$  eGFR decline or ACR  $> 30$  mg/g; as in a traditional "case-control" study design). This is advantageous for the following reasons: 1) the strategy allows for studying multiple endpoints using the same "control" group (ie, the sub-cohort); 2) it bypasses a certain degree of arbitrariness unavoidable when attempting to define the comparison group intended to include only "non-cases" (ie, the inclusion of "false negatives"); 3) the strategy allows a random sample of the cohort for valid cross-sectional comparisons (eg, the association between baseline ACR and biomarkers of CKD and systemic and vascular inflammation and oxidative stress in the cohort random sample); and 4) it allows calculation of hazard ratios using survival models rather than relying on logistic regression and calculation of odds ratios.

The distribution of biomarkers at baseline and during follow-up will be graphed. For biomarkers that are not normally distributed, an appropriate transformation will be performed (eg, log transformation). Mean baseline and change in the levels of these biomarkers will be calculated for participants who experience a  $\geq 30\%$  decline in eGFR and the sub-cohort. Differences will be calculated using ANOVA with weighting to account for the probability of selection into the sub-cohort. Next, we will calculate the association between biomarkers of CKD, systemic and vascular inflammation and oxidative stress with CKD progression using a pseudo-likelihood, weighted Cox regression model. Using the approach of Barlow and Prentice for case-cohort analysis, we will calculate the hazard ratio for a  $\geq 30\%$  decline in eGFR associated with each biomarker separately. Initial models will control for age, race, and sex. Subsequent models will include further adjustment for systolic blood pressure, total and HDL-cholesterol, cigarette smoking, waist circumference, and baseline eGFR and ACR. A final model will include further adjustment for  $\log_{10}$  HIV RNA load and CD4 $^{+}$  T-cell counts.

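### Appendix V, Objective 3 compares kidney cases with a sub-cohort that itself contains cases, so the ANOVA groups overlap: the difference shrinks by the case share and an ordinary standard error is wrong, in this preliminary step only

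*Protocol*

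**What the plan says.** Objective 3 in Appendix V adopts a case-cohort design and explains it: "In a case-cohort design, the comparison group is not defined on the basis of the 'absence' of the outcome". Among the listed advantages, "the strategy allows a random sample of the cohort for valid cross-sectional comparisons". The sub-cohort is therefore drawn without regard to outcome.

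The next paragraph sets out the first comparison: "Mean baseline and change in the levels of these biomarkers will be calculated for participants who experience a" 30% or greater eGFR decline, and for the sub-cohort. The test is then named: "Differences will be calculated using ANOVA with weighting to account for the probability of selection into the sub-cohort". The text does not give the sub-cohort size, the weights, the group to which a case inside the sub-cohort belongs, or a variance estimator. A pseudo-likelihood weighted Cox model for each biomarker follows, and then a mediation analysis.

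The Sample Size section of Appendix V gives the expected case share: "We anticipate an annual event rate of 2.5% based on previous reported results", so "over 4 years, we anticipate 10% of participants will meet our primary outcome of eGFR decline". Detectable differences are given "also for 8% and 15% incidence of eGFR decline" as well. The general analysis plans at the start of the same appendix's statistical section call Objective 3 a case-control design, which would have no overlap.

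**The concern.** ANOVA assumes that the groups are separate and independent. A random sub-cohort contains cases at about the cohort rate, and the plan contrasts all cases with all of the sub-cohort. Cases drawn into the sub-cohort then contribute to both means. This has two consequences. The contrast is diluted, because the comparison mean is pulled toward the case mean. The two means are also positively correlated, and an independent-groups standard error ignores that.

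At stake is the accuracy of the reported biomarker differences and the sensitivity of their tests in the ancillary kidney study's mechanistic objective.

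**Working it through.** **Inputs from the protocol (Appendix V, Sample Size).** At least 2500 participants; 5% lost, leaving 2500 × 0.95 = 2375; two-sided 5% alpha; annual event rate 2.5%; case share p = 10% over 4 years, with 8% and 15% as alternatives; Aim 1A alternative 10% versus 6.4%.

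**Assumed, because not stated.** Sub-cohort size m (250 or 500) or sampling fraction f (10% to 50%); a true case versus non-case difference d (0.25 or 0.30 SD); unit variance.

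**The plan's own figures.** 4 × 2.5% = 10% (9.6% if compounded). For 10% versus 6.4% with 1187.5 per arm, a pooled-variance test has 89.3% power, and 90.7% with 1250 per arm. The stated 90% reproduces. The protocol gives no figure for the ANOVA.

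**Dilution.** The sub-cohort mean is p × (case mean) + (1 − p) × (non-case mean). Hence case mean − sub-cohort mean = (1 − p) × (case mean − non-case mean).

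| Case share | Share of difference retained |
|---|---|
| 8% | 92% |
| 8.2% (pooled 10% and 6.4%) | 91.8% |
| 10% | 90% |
| 15% | 85% |

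In simulation (4000 replicates, N = 2375, f = 10% or 30%), a true 0.30 SD difference was estimated at about 0.275, 0.27 and 0.25 SD for p = 8%, 10% and 15%. Comparing cases with sub-cohort non-cases recovered 0.30.

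**Standard error from overlap alone, no weights.** With D cases:
- Independent-groups variance: 1/D + 1/m
- True variance: 1/D + 1/m − 2p/D

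For D = 250 and p = 0.10:
- m = 250: √0.0080 = 0.0894 against √0.0072 = 0.0849, so 5.4% too large.
- m = 500: √0.0060 = 0.0775 against √0.0052 = 0.0721, so 7.4% too large.

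With 2375 participants and f from 10% to 50%, the excess is 5–8% at p = 8%, 5–10% at p = 10% and 7–14% at p = 15%.

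**Power at d = 0.25, D = 250, p = 0.10.** The overlapping test rejects when the observed difference exceeds 1.96 × the independent-groups SE. The difference has mean 0.25 × 0.90 = 0.225 and the true SE above.
- Overlap, m = 250: Φ((0.225 − 1.96 × 0.0894)/0.0849) = 72.1%.
- Overlap, m = 500: Φ((0.225 − 1.96 × 0.0775)/0.0721) = 84.5%.
- Disjoint, m = 250: SE = √(1/250 + 1/225) = 0.0919, z = 2.72, power 77.7%.
- Disjoint, m = 500: SE = √(1/250 + 1/450) = 0.0789, z = 3.17, power 88.7%.

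The losses are 5.6 and 4.2 points. Using the independent-groups SE as if it were also the true SE gives 71% and 83% for the overlapping test, which exaggerates the loss to about 7 and 6 points. The type I error of the overlapping test is 2 × (1 − Φ(1.96 × 1.054)) = 0.039 at m = 250 and 0.035 at m = 500. Simulation of the same scenario gave 0.039 and 0.033.

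**Effect of the unstated weights, overlap retained (simulation, p = 8% to 15%).**
- 1/f used as variance weights, f = 10% or 30%: SE about 1.5 to 2.0 times too large.
- 1/f used as frequency weights, f = 10%: SE 18–27% too small, type I error 0.11–0.15.
- 1/f used as frequency weights, f = 30%: SE within about 4% of correct.
- Disjoint groups with an unequal-variance SE: SE ratio 0.98–1.02, type I error 0.045–0.059.

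**The case against.** The best defence is that the planned test is weighted, and weighting may be meant to resolve the overlap. If cases carry weight 1 and sub-cohort non-cases carry 1/f, with each person entered once, there is neither overlap nor dilution. That is a legitimate analysis, but the text does not describe it: it names the two groups as the cases and the sub-cohort, and says only that selection into the sub-cohort is weighted. The point stands on the wording. The objection does show that the direction of the standard-error problem cannot be fixed from the documents.

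A second defence is that case versus whole cohort is a valid contrast in its own right, and that the protocol has reasons for not restricting the comparison group: one group serves several endpoints, and defining non-cases risks false negatives. This is fair as far as the estimate goes. The dilution is then a matter of which contrast is reported, and it is zero when cases and non-cases do not differ. It does not rescue a standard error that treats shared participants as independent.

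A reader might infer that biomarkers missed here would drop out of the mechanism argument. The documents do not support that. The Cox model is fitted for each biomarker separately, and the mediation analysis takes each biomarker alone and all together; neither is conditional on the ANOVA. A reader might also infer that the overlap inflates false positives. On its own it does the reverse.

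**Conclusion.** The concern holds in a limited form. As worded, the comparison uses overlapping groups. The estimated difference is 8% to 15% smaller than the case versus non-case difference on the protocol's incidence range; this follows from the wording and the stated incidence alone. An ordinary ANOVA standard error is wrong. From overlap alone it is about 5% to 7% too large at 10% incidence with 250 cases, costing roughly 4 to 6 points of power. Those two figures rest on an assumed sub-cohort of 250 or 500, and the power figure also on an assumed 0.25 SD difference and no weights. Allowing for the 5% loss would leave about 238 cases rather than 250.

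The damage is confined to a preliminary comparison in the third objective of an ancillary study. There is no bias under the null, nothing later depends on the result, and the case-cohort Cox model is unaffected. This is a minor correction, worth making because it is cheap.

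**What to change.** In Appendix V, Objective 3, state the sub-cohort size and weights, and compare cases with sub-cohort members who are not cases for that endpoint, counting each person once, with a robust or design-based variance. Do not use 1/f as frequency weights. Even with disjoint groups (N = 2375, p = 10%), that makes the standard error about 27% too small at f = 10% (type I error about 0.155) and about 10% too small at f = 30% (about 0.078). In a simple random sub-cohort every non-case has the same 1/f, so the weight does not change the non-case mean in any event.

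Keep the full sub-cohort for the pseudo-likelihood Cox model and for cross-sectional description. Reconcile the case-control label in the general analysis plans with the case-cohort design in Objective 3.

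The cost is a sentence or two of text and a group indicator in the code, with no new data. There is one small downside: the non-case set will differ between the eGFR-decline and ACR endpoints, which gives up part of the shared-comparison-group convenience for this step.
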